Institution Name: _____	

By my signature, I agree to personally supervise the conduct of this study at my study site and to ensure its conduct is in compliance with the protocol, informed consent, Institutional Review Board (IRB)/Ethics Committee (EC) procedures, instructions from Celgene representatives, the Declaration of Helsinki, International Council for Harmonisation (ICH) Good Clinical Practices Guidelines, and local regulations governing the conduct of clinical studies.
	

COORDINATING PRINCIPAL INVESTIGATOR SIGNATURE PAGE

Signature of Coordinating Principal Investigator _____	dd mmm yyyy _____
Printed Name of Coordinating Principal Investigator	
Institution Name: _____	
By my signature, I agree the protocol has been written to comply with ICH Good Clinical Practices guidelines and agree to offer guidance throughout the study as needed.	

PROTOCOL SUMMARY

Study Title

A Phase 2, Randomized, Double-blind, Placebo-controlled, Multicenter, Dose-finding Study to Evaluate the Efficacy and Safety of CC-90001 in Subjects with Non-alcoholic Steatohepatitis (NASH) and Liver Fibrosis

Indication

Non-alcoholic steatohepatitis (NASH)

Objectives

The effect of oral (PO) CC-90001, administered once daily (QD), compared with placebo, will be evaluated in subjects with NASH and Stage 2 or Stage 3 fibrosis.

Primary Objective

The primary objective of the study is to evaluate the effect of oral CC-90001, administered QD, compared with placebo, on liver histology in subjects with NASH and Stage 2 or Stage 3 fibrosis.

Secondary Objective(s)

- To evaluate the effects of oral CC-90001, administered QD, compared with placebo, in subjects with NASH and Stage 2 or Stage 3 fibrosis, on:
 - Additional liver biopsy-based endpoints
 - Liver biochemistry-based endpoints
 - Metabolic parameters-based endpoints
 - Dose response
 - Safety and tolerability
 - Pharmacokinetics (PK)

Study Design

This is a Phase 2, randomized, double-blind, placebo-controlled, multicenter, multinational, dose-finding study evaluating the efficacy of treatment with CC-90001, compared with placebo, in NASH subjects with Stage 2 or Stage 3 liver fibrosis. Safety, PK, [REDACTED] of CC-90001 compared to placebo will be evaluated.

Approximately 180 adult male and female subjects with a confirmed diagnosis of NASH and Stage 2 or Stage 3 fibrosis will be randomized 1:1:1 to treatment with oral CC-90001 (200 mg QD, 60 subjects; 400 mg QD, 60 subjects) or matching placebo (60 subjects) for 52 weeks. Prior to the implementation of Protocol Amendment 4, subjects were also randomized into a 100 mg QD dose group. The subjects who were previously randomized to the 100 mg dose group will remain in the 100 mg dose group throughout the study. It is expected that approximately 10-15 subjects will have been randomized to the 100 mg group at time of implementation of Protocol Amendment 4. Thus, a total of approximately 195 subjects will participate in the study.

Randomization will be stratified by liver fibrosis stage (Stage 2/Stage 3) and by the presence of Type 2 Diabetes Mellitus (DM) (yes/no). To ensure enrollment of a suitable number of subjects with Stage 3 fibrosis, up to 15 subjects with Stage 2 fibrosis may be enrolled per arm. Randomization, treatment assignment and stratification will be managed by an interactive web response system (IWRS).

An independent external data monitoring committee (DMC) will be responsible for review of the interim analyses data and will make recommendations to the Sponsor, who will be responsible for final decision-making. An unblinded interim analysis will be performed after approximately 50% of subjects complete 52 weeks of placebo-controlled treatment phase (as described in the DMC Charter).

Subjects who sign informed consent form (ICF) prior to the implementation of Protocol Amendment 4, will have an option to participate in a double-blind active treatment phase. After 52 weeks of placebo-controlled treatment all placebo subjects will be re-randomized 1:1 by IWRS to the 200 mg, or 400 mg QD dose groups at Week 54. Prior to the implementation of Protocol Amendment 4, subjects were also re-randomized into a 100 mg QD dose group. The subjects who were previously re-randomized to the 100 mg dose group will remain in the 100 mg dose group. Subjects who were initially randomized to active

treatment arms will remain in their assigned dose groups through the end of the double-blind active treatment phase.

Subjects who sign ICF after the implementation of Protocol Amendment 4 will receive treatment in a double-blind placebo-controlled treatment phase only.

All subjects who complete the study treatment phases and those subjects who discontinue investigational product (IP) prior to the completion of the study will participate in the 4-week Post-treatment Observational Follow-up Phase.

The study will be conducted in compliance with International Council for Harmonisation (ICH) Good Clinical Practices (GCPs).

Study Population

The study population includes adult male and female subjects, ≥ 18 years of age, with a confirmed diagnosis of NASH and Stage 2 or Stage 3 fibrosis based upon the NASH Clinical Research Network (CRN) Histologic Scoring System and a Nonalcoholic Fatty Liver Disease (NAFLD) Activity Score (NAS) of 4 or higher, with a score of at least 1 for each of the three components (steatosis, hepatocellular ballooning, and lobular inflammation).

Length of Study

Subjects who sign ICF prior to the implementation of Protocol Amendment 4 and elect not to participate in the active treatment phase, or subjects who sign ICF after the implementation of Protocol Amendment 4:

The study will have a total duration of up to 66 weeks. The study will consist of an up to 10-week Screening Phase; a 52-week Double-blind Placebo-controlled Treatment Phase; and a 4-week Post-Treatment Observational Follow-up Phase.

Subjects who sign ICF prior to the implementation of Protocol Amendment 4 and elect to participate in the active treatment phase:

The study will have a total duration of up to 116 weeks. The study will consist of an up to 10-week Screening Phase; a 52-week Double-blind Placebo-controlled Treatment Phase; a 50-week Double-blind Active Treatment Phase; and a 4-week Post-Treatment Observational Follow-up Phase.

The End of Trial is defined as either the date of the last visit of the last subject to complete the post-treatment follow-up, or the date of receipt of the last data point from the last subject that is required for primary, secondary [REDACTED] analysis, as prespecified in the protocol, whichever is the later date.

Study Treatments

All subjects will be instructed to take 3 tablets once daily, approximately the same time of day (preferably in the morning), with or without food. All IP treatment allocation will be handled by IWRS.

- **52-Week Double-blind Placebo-controlled Treatment Phase:**
 - 100 mg PO QD CC-90001 (for subjects who are randomized prior to implementation of Protocol Amendment 4)

- 200 mg PO QD CC-90001
- 400 mg PO QD CC-90001
- Matching Placebo for 100 mg and 200 mg tablets
- **50-Week Double-blind Active Treatment Phase (only for subjects who participate in the active treatment phase):**
 - 100 mg PO QD CC-90001 (for subjects who are randomized or re-randomized prior to implementation of Protocol Amendment 4)
 - 200 mg PO QD CC-90001
 - 400 mg PO QD CC-90001

Overview of Efficacy Assessments

- NASH CRN histological score (liver fibrosis score and NAS)

- Liver biochemistry
 - Aspartate aminotransferase (AST)
 - Alanine aminotransferase (ALT)
 - Gamma (γ)-glutamyl transferase (GGT)
- Metabolic parameters
 - Serum lipids (total cholesterol, low-density lipoprotein [LDL], high-density lipoprotein [HDL], and triglycerides)

- Progression to cirrhosis (Stage 2 and Stage 3 subjects only)

Overview of Key Safety Assessments

- Adverse events
- Physical examination, vital signs, and weight
- Clinical laboratory tests including serum chemistry, hematology, and urinalysis (including urine cytology)
- Pregnancy testing
- 12-lead electrocardiogram

- Assessments of concurrent therapies and procedures

Statistical Methods

The estimated improvement on ≥ 1 fibrosis score in Stage 3 subjects of 45% for CC-90001 group and 20% for the placebo group is based on a Phase 2 study of selonsertib, which reported a 23% treatment difference (43% in the selonsertib 18 mg group versus 20% in the simtuzumab group—a compound that was not demonstrated to be effective for NASH with a treatment response similar to placebo from other clinical trials) (Loomba, 2018; Neuschwander-Tetri, 2015).

With the above assumed treatment responses for the primary endpoint between the highest CC-90001 dose group and the placebo, and further assuming a similar treatment effect in Stage 2 subjects, the sample size of 60 for the placebo, 200 mg, and 400 mg treatment group and an expected sample size of 10-15 for the 100 mg treatment group provides the ability to determine a dose response with 80% power, and 5% type I error rate. It also provides high sensitivity to determine a Minimum Effective Dose (MED) when a range of response rates and clinically significant effects are assumed.

The efficacy analyses will be performed using the Full Analysis Set (FAS), defined as all subjects who are randomized and received at least one dose of IP. The treatment comparison will be made between each of the CC-90001 treatment groups and placebo. No adjustment for multiple comparisons will be made.

The binary efficacy endpoints will be summarized using counts and percentages. The treatment comparisons will be performed using the Cochran–Mantel–Haenszel (CMH) test adjusting for the stratification factors as appropriate. Missing values due to early termination will be imputed using data collected at the early termination visit if available; otherwise missing values will be imputed using the non-responder imputation (NRI) method.

The continuous efficacy endpoints will be summarized using mean, standard deviation (SD), median, minimum, maximum, and number of observations analyzed. The treatment comparisons will be performed using a mixed model of repeated measures (MMRM) as the primary analysis method and an analysis of covariance (ANCOVA) model as sensitivity analysis method for all continuous secondary efficacy endpoints.

The safety analyses for the 52-week placebo-controlled treatment phase will be performed using descriptive statistics based on the safety population, defined as all subjects who are randomized and receive at least one dose of IP. The safety analyses will also be performed for the CC-90001 exposure period for subjects who receive at least one dose of CC-90001, which will include safety data during the placebo-controlled treatment phase and active treatment phase.

An unblinded interim analysis will be performed after approximately 50% of subjects complete 52 weeks of treatment (as described in the DMC Charter).

TABLE OF CONTENTS

TITLE PAGE.....	1
PROTOCOL SUMMARY	6
1. INTRODUCTION.....	19
1.1. Disease Background	19
1.2. Compound Background.....	19
	
1.3. Rationale	27
1.3.1. Study Rationale and Purpose	27
1.3.2. Rationale for the Study Design	28
1.3.3. Rationale for Dose, Schedule and Regimen Selection	28
	
2. STUDY OBJECTIVES AND ENDPOINTS.....	30
3. OVERALL STUDY DESIGN	35
3.1. Study Design	35
3.2. Study Duration for Subjects.....	38
3.2.1. Early Termination Visit	38
3.2.2. Lost to Follow-up	38
3.3. End of Trial	38
4. STUDY POPULATION	40
4.1. Number of Subjects	40
4.2. Inclusion Criteria	40
4.3. Exclusion Criteria	42
5. TABLE OF EVENTS.....	46
6. PROCEDURES	53
6.1. Screening Phase.....	53
6.2. Treatment Period	55
6.2.1. Unscheduled Visits	57
6.3. Early Termination.....	57
6.4. Post-treatment Observational Follow-up Phase	58

6.5. Safety Assessments..... 58
6.5.1. Physical Examination 58
6.5.2. Electrocardiogram 59
6.5.3. Clinical Laboratory Assessments 59
6.5.4. Action Plan for Monitoring Potential Hepatotoxicity 60

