2. STUDY OBJECTIVES AND ENDPOINTS

Table 1: Study Objectives

Primary Objective
The primary objective of the study is to evaluate the effect of oral CC-90001, administered once daily (QD), compared with placebo, on liver histology in subjects with nonalcoholic steatohepatitis (NASH) and Stage 2 or Stage 3 fibrosis.
Secondary Objective(s)
The secondary objectives are: 
• To evaluate the effects of oral CC-90001, administered QD, compared with placebo, in subjects with NASH and Stage 2 or Stage 3 fibrosis, on:
- Additional liver biopsy-based endpoints- Liver biochemistry-based endpoints- Metabolic parameters-based endpoints- Dose response- Safety and tolerability- Pharmacokinetics (PK)

Table 2: Study Endpoints

Endpoint	Name	Description	Timeframe
Primary	Liver fibrosis score	Proportion of subjects who achieve a ≥ 1 stage improvement in liver fibrosis using the nonalcoholic steatohepatitis (NASH) clinical research network (CRN) Histological Scoring System	Week 52
Secondary	Combined assessment of liver fibrosis score and steatohepatitis	Proportion of subjects who achieve a ≥ 1 stage improvement in liver fibrosis and no worsening of steatohepatitis (no worsening of lobular inflammation or hepatocellular ballooning score)	Week 52
	Nonalcoholic fatty liver disease (NAFLD) activity score (NAS)	Proportion of subjects with an improvement of ≥ 2 points in the total NAS in more than one category of steatosis, lobular inflammation, and hepatocellular ballooning, and no worsening of liver fibrosis	Week 52
	Resolution of NASH	Proportion of subjects who demonstrate absence of ballooning, and lobular inflammation score of 0 or 1	Week 52
	Resolution of NASH without worsening of liver fibrosis	Proportion of subjects who demonstrate absence of ballooning, and lobular inflammation score of 0 or 1 and no worsening of liver fibrosis	Week 52
	Progression to cirrhosis	Proportion of subjects who progress to cirrhosis	Week 52
	Liver biochemistry	Change from Baseline in serum aspartate aminotransferase (AST), alanine aminotransferase (ALT) and γ -glutamyl transferase (GGT)	through Week 52
	Metabolic parameters	Change from Baseline in total cholesterol, low density cholesterol (LDL) high density cholesterol (HDL), and triglycerides	through Week 52
	Dose response	Dose-related changes in the primary and secondary endpoints	through Week 24 (secondary endpoints); through Week 52 (primary and secondary endpoints)

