3.2.1. Early Termination Visit

The Early Termination (ET) Visit is based on the subject's withdrawal from the study prior to the Week 102 Visit for subjects who participate in the active treatment phase or prior to the Week 52 Visit for subjects who do not participate in the active treatment phase. In addition, the Investigator may discontinue the subject from the study at any time based on his/her assessment of clinical efficacy and/or safety. The decision to discontinue a subject remains the responsibility of the treating physician and will not be delayed or refused by the sponsor. When a subject withdraws or is discontinued from the study treatment, every effort should be made to complete as many safety and efficacy assessments as reasonably appropriate. Refer to the Table of Events ([Table 3](#)) for the assessments to be performed at the ET Visit. The ET Visit should be scheduled as soon as possible after the decision is made to permanently discontinue study treatment.

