- ^d Visit 5 Week 8 and Visit 7 Week 16 will be remote visits. Central laboratory tests, target physical examination, vital sign and weight will not be performed during these remote visits. However, if laboratory tests and/or physical examination is needed based on the Investigator's clinical judgement, an unscheduled visit should be performed at the investigational site. Urine pregnancy test kits will be provided to the subjects at Visit 4 Week 4 and Visit 6 Week 12. At Visit 5 Week 8 and Visit 7 Week 16 subjects will perform urine β -hCG test at home. IP will be dispensed at Visit 4/Week 4 and Visit 6/Week 12 for these 2 visits.
- ^e Urine pregnancy test will be performed to assess subject eligibility prior to the first administration of IP if a serum pregnancy test was not obtained within 72 hours prior to dosing (negative results required for IP administration).
- ^f Subjects who do not have a historical biopsy will undergo a liver biopsy procedure for study eligibility. The independent histopathologists will review the liver biopsy specimens to assess whether the subject meets the histological inclusion criteria. Screening liver biopsy will serve as the Baseline assessment. Subjects who discontinue after Week 20 and before Week 52 will undergo a liver biopsy procedure at ET Visit. IP should be stopped 7-10 days prior to Week 53 or ET Visit biopsy and restarted 7 days after biopsy at Week 54 if subjects participate in the active treatment phase.

^j First dose of IP should be administered at the investigative site.

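### Does non-responder imputation leave progression to cirrhosis without a usable missing-data rule?

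*Combined protocol and SAP*

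**What the plan says.** The Statistical Methods part of the Protocol Summary treats binary endpoints as a class. It begins "The binary efficacy endpoints will be summarized using counts and percentages" and then sets the missing-data rule. The first step is "Missing values due to early termination will be imputed using data collected at the early termination visit if available". The fallback, for subjects with no such data, reads "otherwise missing values will be imputed using the non-responder imputation (NRI) method".

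Progression to cirrhosis belongs to that class. It appears in the Summary's overview of efficacy assessments, and Table 2 lists it as a Week 52 secondary endpoint: "Proportion of subjects who progress to cirrhosis".

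Section 9.6.1.1 spells out the same rule for the primary endpoint, a favourable response. Section 9.6.1.2 analyses the binary secondary endpoints on the FAS, in a similar way to the primary, with the CMH test. It states no direction of imputation. Section 9.1 calls Section 9 an outline and sends the details to a separate SAP, whose text is not in the supplied document.

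Two provisions limit who can be affected. Table 3, footnote f, says: "Subjects who discontinue after Week 20 and before Week 52 will undergo a liver biopsy procedure at ET Visit". Section 3.2.1 adds that for anyone withdrawn "every effort should be made to complete as many safety and efficacy assessments as reasonably appropriate".

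**The concern.** For fibrosis improvement or NASH resolution, failing to meet the endpoint and failing on treatment are the same thing, so non-responder imputation has only one meaning. For progression to cirrhosis they are opposites. Taken literally, a missing subject has not met the endpoint and counts as not progressed, which flatters an arm with more missing biopsies. Taken as treatment failure, the subject counts as progressed, which penalises that arm.

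Two programmers working from the same sentence could therefore produce different tables. Subjects who leave by Week 20 have no specified follow-up biopsy but stay in the FAS denominator, so the case can arise. The stated sensitivity analyses do not clearly cover it: the per-protocol analysis is named for the primary endpoint and ANCOVA for the continuous ones. At stake are the reported progression percentages and, if missingness differs by arm, the treatment difference.

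**Working it through.** The protocol states no figure that depends on this coding, so there is nothing to reproduce. The check measures how far apart the two codings can be and whether one is clearly better.

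**Inputs.** The arm sizes come from the Protocol Summary and Section 9.3: "the sample size of 60 for the placebo, 200 mg, and 400 mg treatment group and an expected sample size of 10-15"; the last figure refers to the 100 mg arm. Rates of progression and of missing biopsies are not given; those below are assumed.

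**Formulas.** Let p be the progression rate among observed subjects and m the missing fraction, with 1 = active and 0 = placebo.

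- Coding A (missing = not progressed): rate = p(1 - m).
- Coding B (missing = progressed): rate = p(1 - m) + m.
- Within an arm, B - A = m. For the treatment difference, B - A = m1 - m0, whatever p is.
- Under CMH weighting the same identity holds in each stratum, so the gap is the weighted average of the stratum differences in missingness.

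**Size per subject.** One excess missing biopsy moves the answers apart by 1/60 = 1.67 points in a full arm. In the 100 mg arm it is 1/15 = 6.7 to 1/10 = 10 points.

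**Equal true progression in both arms, 60 per arm.** SE = sqrt[r0(1 - r0)/60 + r1(1 - r1)/60]. Rates are placebo v active; differences are active minus placebo, in points.

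| p | Missing, placebo v active | Coding A | Coding B | Gap |
|---|---|---|---|---|
| 10% | 5% v 10% | 9.5% v 9.0%: -0.50 (SE 5.3) | 14.5% v 19.0%: +4.50 (SE 6.8) | 5.0 |
| 15% | 5% v 10% | 14.25% v 13.5%: -0.75 (SE 6.3) | 19.25% v 23.5%: +4.25 (SE 7.5) | 5.0 |
| 15% | 10% v 25% | 13.5% v 11.25%: -2.25 (SE 6.0) | 23.5% v 36.25%: +12.75 (SE 8.3) | 15.0 |
| 10% | 10% v 10% | 9.0% v 9.0%: 0 | 19.0% v 19.0%: 0 | 0 |

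The true difference is zero in every row. Coding A errs by at most 0.4 SE, coding B by up to 1.5 SE.

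**A true benefit, with assumed counts.** Take 8 v 4 observed progressions and 3 v 7 missing biopsies, placebo v active.

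- Coding A: 8/60 = 13.3% v 4/60 = 6.7%, difference -6.7.
- Coding B: 11/60 = 18.3% v 11/60 = 18.3%, difference 0.0.
- Observed biopsies only: 8/57 = 14.0% v 4/53 = 7.5%, difference -6.5.

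**What this rests on.** The table assumes that missing subjects progress at the same rate as observed ones. More generally, let q be the true progression rate among the missing, the same in both arms. The true arm rate is p(1 - m) + qm, so coding A distorts the treatment difference by -q(m1 - m0) and coding B by (1 - q)(m1 - m0). Coding A is closer to the truth whenever q is below one half. Coding B also requires that a Stage 2 subject who left by Week 20 be counted as Stage 4, a two-stage worsening.

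**The case for a change.** The strongest argument for acting is that the ambiguity is real and cheap to remove. The Summary states the rule for the whole class, so a SAP that copies the sentence copies the ambiguity. Section 11.1.1 discontinues subjects who develop decompensated liver disease; if such a subject has no usable biopsy, the literal coding records no progression, which is hard to defend. Section 11.1.1 and Appendix C also discontinue subjects for drug-related events and liver-test elevations, so dropout could differ by arm. An unblinded interim analysis is planned (Section 9.8), which favours settling the coding beforehand.

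Much of this stands. No supplied text gives the direction, and the arithmetic is exact. It also makes sense to declare the coding before anyone sees unblinded results. The case does not show that a stated rule gives a wrong answer. Arm-dependent missingness is possible but not documented. The few decompensated subjects are a reason to look at individual cases; they do not justify counting every early leaver as cirrhotic. Exempting this endpoint from non-responder imputation while defending missing = progressed as the intent of that method would also be inconsistent: if that is the intent, the present wording already gives that coding.

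**Conclusion.** The observation is correct, but no change to the plan follows. What is missing is a coding convention for one of several secondary endpoints. It concerns mainly early terminators without a usable biopsy, in a section that leaves such details to the SAP. An analyst writing the derivation of this endpoint would have to choose a direction and would ordinarily report the number of missing biopsies by arm beside the result.

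The possible effect is bounded. The two answers differ by the between-arm difference in missingness: 1.67 points per excess missing biopsy in an arm of 60, 5 points at 5% v 10% missing, and 15 points at an assumed extreme of 10% v 25%. With equal missingness the treatment difference agrees under both codings and only the arm percentages move, for example 9% or 19% in each arm.

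Fixing missing = progressed would be a trade-off. It guards against flattering an arm with more dropout, but gives the larger artefact unless at least half of the missing subjects truly progressed. The fibrosis primary endpoint, the sample size and the primary dose-response analysis are unaffected. Section 9.6.1 treats all p-values as nominal, and the supplied text ties no decision rule to this endpoint. All progression and missingness rates here are assumptions; only the identity and the per-subject steps are exact.
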